14.3. Analysis Populations

Safety Population:

All subjects who are administered any test article excluding subjects who drop out prior to administering any test article. At least one observation should be recorded.

Per-Protocol Population:

All subjects who successfully complete all visits and do not substantially deviate from the protocol as determined by the trial cohort review committee prior to database hard lock. Justification for the exclusion of subjects with protocol deviations from the per-protocol population set will be documented in a memo to file.

Intent-to-Treat (ITT) Population:

All randomized subjects regardless of actual treatment and subsequent withdrawal from the study or deviation from the protocol. At least one observation should be recorded.

14.4. Level of Statistical Significance

All co-primary safety, co-primary efficacy, and secondary hypotheses will be tested using a multibranch gate keeping strategy. Study hypotheses will be evaluated sequentially as follows:

Clinical Study Protocol

CR-6521, v 3.0

■

JJVC CONFIDENTIAL

Clinical Study Protocol
Johnson & Johnson Vision Care, Inc.

First, co-primary safety hypotheses will be evaluated using 95% central posterior credible intervals for the probability of grade 3 or higher SLFs and acceptable lens fitting. Both hypotheses must be met in order to test co-primary efficacy hypotheses. Each co-primary efficacy hypothesis will be tested with a type I error rate of 5%. All co-primary safety and co-primary efficacy hypotheses must be met to test any secondary hypotheses. Secondary hypotheses will be tested utilizing a Bonferroni adjustment¹⁰ with an overall two-sided family-wise type I error rate of 5% (2.5% individually).

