2.3. Hypotheses

Co-Primary Safety Hypotheses:

1. The percentage of eyes with one or more clinically significant, study-lens related, slit-lamp findings (Grade 3 or 4) following wear of the test lenses will be less than 5%.
2. At least 80% of lens fits will be acceptable at the dispensing visit.

Both co-primary *safety* hypotheses must be met in order to test any co-primary *efficacy* hypotheses.

Co-Primary Efficacy Hypotheses:

1. After approximately 1-week of wear, the mean monocular, high-luminance, high-contrast distance visual acuity for the test lens will be lower than 0.00 logMAR (equivalent to 20/20 Snellen visual acuity).
2. Following lens settling (at least 15 minutes) at the dispensing visit, at least 80% of lens fits will have absolute rotation less than or equal to 10 degrees.
3. Following lens settling (at least 15 minutes) at the dispensing visit, at least 80% of lens fits will have lens rotational stability with blink less than or equal to 5 degrees.
4. After approximately 1 week of wear, the mean overall CLUE™ Vision score for the test lens will be statistically greater than 62 points.

All safety and efficacy co-primary hypotheses must be satisfied in order to meet the study objectives and to test any secondary hypotheses.

Secondary Hypotheses:

1. After approximately 1 week of wear, the mean overall CLUE™ Handling score for the test lens will be greater than 61 points with 95% statistical confidence.
2. After approximately 1 week of wear, the mean overall CLUE™ Comfort score for the test lens will be greater than 58 points with 95% statistical confidence.

Clinical Study Protocol
Johnson & Johnson Vision Care, Inc.

Exploratory Hypotheses:

1. After approximately 1 week of wear, the test lens will be non-inferior to the control lens with respect to at least one of the following subjective questionnaire items asked at the follow-up visit:
 - a. Ability to see comfortably while driving during the day
 - b. My vision was clear enough to allow me to drive at night
 - c. Reduction in the feeling of tired eyes from using a computer or other digital device

A non-inferiority margin of 10% will be used.

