Sample size calculations for handling and comfort scores were calculated separately using one-sided, one-sample mean t-test, with a type I error rate of 2.5% for each hypothesis. To preserve the overall study power, each endpoint was powered to 99%. Sample size calculations were performed using the *One-Sample T-Tests for Superiority by a Margin* procedure in Power Analysis & Sample Size (PASS2021) software Version 21.0.6 (NCSS LLC, Kaysville UT).⁹

Table 9 below, displays sample size estimates by endpoint. As indicated below, co-primary safety endpoints were powered ~99% individually yielding a combined power of ~98%. With respect to co-primary efficacy, each hypothesis, except for CLUE Vision (powered to 91%) was powered to ~99%, which provided a combined power of ~88%. Therefore, the overall combined study power for co-primary safety and co-primary efficacy hypotheses is ~86% and is considered reasonable to support any conclusions from these analyses. Furthermore, secondary endpoints were powered to achieve at least 99% statistical power. This was considered to have a minimal impact on overall study power because of the multibranch gate keeping approach being implemented.

Table 9: Sample Size Estimates for Co-Primary Safety, Efficacy and Secondary Endpoints

Endpoint Type	Endpoint	Test Type	Sample Size	Power (%)
Primary Safety	Grade 3 or Higher SLFs (5%)	Statistically less than (5%)	100	99
	Acceptable Lens Fitting (%)	Statistically greater than (80%)	100	99
Primary Efficacy	Distance (4m) Monocular Visual Acuity (logMAR)	Superiority (0.00)	9	99
	Absolute Toric Rotation < 100	Statistically greater than (80%)	40	99
	Lens Stability with Blinks 5°	Statistically greater than (80%)	100	99
	CLUE Vision Scores	Superiority (62)	144	91
Secondary	CLUE Handling Scores	Superiority (61)	135	97
	CLUE Comfort Scores	Superiority (58)	135	97

While only a total of 144 subjects are required to complete the study based on the sample size calculations, the target enrollment is approximately 180 subjects with a target completion of at least 165 subjects. Data collected from this study may be utilized to perform a meta-analysis at a later date, therefore, the target completion for this study was increased to 165 subjects to accommodate this possibility.

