14.6. Secondary Analysis

CLUE Handling and Comfort Scores

CLUE Handling and Comfort scores after 1-week of lens wear will be analyzed separately using a linear mixed model adjusting for baseline scores as a covariate. Sequence of lens wear, lens type and period will be included in the model as fixed effects. Subject characteristics such as, gender, age and/or cylinder power made be included in the model if appropriate. Site ID will be included in the model as a random effect (G-side). The residual error between measurements within the same subject will be modeled using an unstructured (UN) covariance structure. If the model fails to converge with a UN covariance, then a compound systemic (CS) covariance structure will be used. The Kenward and Roger Method will be used for the denominator degrees of freedom.¹¹ CLUE Handling and Comfort scores for each study lens will be estimated using 97.5% confidence intervals (CI) constructed for the least-square means (LSM).

Secondary Hypothesis 1:

The null and alternative hypothesis to test for superiority of CLUE Handling score for the test lens relative to the threshold 61 are as follows:

$$\begin{aligned} H_0: \mu_{TTTTTTTT} &\leq 61 \\ H_A: \mu_{TTTTTTTT} &> 61 \end{aligned}$$

Where $\mu_{TTTTTTTT}$, represents the population mean for test lens after 1 week of lens wear with respect to CLUE Handling scores. Superiority will be declared if the lower limit of the 97.5% CI is above 61.

Secondary Hypothesis 2:

The null and alternative hypothesis to test for superiority of CLUE Comfort score for the test lens relative to the threshold 58 are as follows:

$$\begin{aligned} H_0: \mu_{TTTTTTTT} &\leq 58 \\ H_A: \mu_{TTTTTTTT} &> 58 \end{aligned}$$

Where $\mu_{TTTTTTTT}$, represents the population mean for test lens after 1 week of lens wear with respect to CLUE comfort scores. Superiority will be declared if the lower limit of the 97.5% CI is above 58.

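### The two secondary CLUE hypotheses use single-step Bonferroni; Holm would control the same 5% family-wise error and add about 1 to 10 points of Handling power, depending on which inputs hold

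*Combined protocol and SAP*

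**What the plan says.** Section 14.4 opens the secondary family only after every co-primary safety and efficacy hypothesis has been met. For that family it says "Secondary hypotheses will be tested utilizing a Bonferroni adjustment", "with an overall two-sided family-wise type I error rate of 5% (2.5% individually").

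Section 14.6 turns this into one fixed rule per endpoint, and neither rule depends on the result of the other:

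- Handling: "Superiority will be declared if the lower limit of the 97.5% CI is above 61".
- Comfort: "Superiority will be declared if the lower limit of the 97.5% CI is above 58".

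The thresholds match section 2.3: "the mean overall CLUE™ Handling score for the test lens will be greater than 61 points" and "the mean overall CLUE™ Comfort score for the test lens will be greater than 58 points". No step-down or reuse of alpha within the secondary family is described.

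The sample-size text in 14.2 is on a different footing. The secondary calculations "were calculated separately using one-sided, one-sample mean t-test", "with a type I error rate of 2.5% for each hypothesis". A two-sided 97.5% CI corresponds to 1.25% in the relevant tail, not 2.5%. Table 9 gives 97% power at n = 135 for both endpoints, while the text of 14.2 claims at least 99%.

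**The concern.** Because the secondaries are reached only when all co-primaries succeed, the full two-sided 5% is available to this two-member family. Under single-step Bonferroni, once one endpoint has passed, the other is still held to 1.25% in its tail, although 2.5% could then be used with the same family-wise protection.

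Table 8 suggests this may matter. Comfort sits 9.9 points above its threshold (67.9 against 58) and Handling only 4.4 points above (65.4 against 61), both with SD 21.50. On those figures Comfort passes almost surely, and Handling is the endpoint that would benefit. At stake is the chance of failing a lens that does meet the handling requirement. The primary objectives are not affected.

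**Working it through.** **Inputs.** Table 8: Handling 65.4 (21.50), Comfort 67.9 (21.50), Vision 67.4 (19.67). Thresholds 61, 58 and 62 (section 2.3). Sample sizes: 135 and 144 (Table 9), 165 target completers (14.2), and 180 × 0.9 = 162 (enrolment target less the synopsis's 10% dropout).

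**Formula.** One-sample t-test: power = P(T > t(1−α, n−1)), where T is noncentral t with n−1 degrees of freedom and noncentrality δ = (mean − threshold)/SD × √n. All powers are conditional on the co-primary hypotheses being met.

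**The plan's own figures.**

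- Vision, n = 144: δ = 5.4/19.67 × 12 = 3.29. At one-sided 2.5% this gives 90.5%, against 91% in Table 9. The formula reproduces that row.
- Handling, n = 135: δ = 4.4/21.5 × √135 = 2.38. Power is 76.5%, 65.6% and 54.5% at one-sided 5%, 2.5% and 1.25%. None is near 97%.
- Comfort, n = 135: δ = 9.9/21.5 × √135 = 5.35. Power is about 99.9% or more at all three levels, again not 97%.

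So Table 8 as printed reproduces neither secondary row of Table 9.

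**Bonferroni against Holm on Table 8, n = 165.** Handling δ = 4.4/21.5 × √165 = 2.63; Comfort δ = 9.9/21.5 × √165 = 5.91.

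- Bonferroni (one-sided 1.25%): Handling 64.3%, Comfort 99.99%.
- Holm: Handling passes at 1.25%, or at 2.5% if Comfort has passed at 1.25%. Handling power at 2.5% is 74.3%. Whatever the correlation, Holm power is at least 0.7433 + 0.9999 − 1 = 0.743, and it cannot exceed 0.743. Simulation at correlations 0 and 0.5 gave 74.2% to 74.5%.
- The probability that both pass moves with Handling, from about 64% to 74%.

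Handling power at other sample sizes:

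| n | Bonferroni | Holm |
|---|---|---|
| 135 | 54.5% | about 65.5% |
| 144 | 57.7% | 68.4% |
| 162 | 63.4% | 73.5% |
| 165 | 64.3% | 74.3% |

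**Error control.** If both nulls are true, Holm makes an error only when the smaller p-value clears the Bonferroni level. If one null is true, that endpoint is tested at two-sided 5% at most, or 2.5% in the direction of a claim. Simulated one-directional error was 2.49% with both nulls true and 2.5% with only the Handling null true. That is the plan's 5% on its two-sided scale.

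**Sensitivity of the gain, n = 165.**

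- Assumed residual SD 18: δ = 3.14, 80.9% to 87.7% (6.8 points).
- Assumed residual SD 15: δ = 3.77, 93.3% to 96.3% (3.0 points).
- If Table 9's 97% at n = 135 is right at one-sided 2.5%, the implied effect size is 0.333. Handling then goes from 97.7% to at most 98.9% (1.2 points). If the 97% was computed at one-sided 5% (effect size 0.305), the gain is at most 97.35 − 95.01 = 2.3 points.
- If each secondary test is meant at one-sided 2.5%, as 14.2 words it, rather than at the 97.5% CI rule, Table 8 gives 74.3% to 83.5%.

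**The case against.** The strongest reply is that nothing here is wrong. Bonferroni is pre-specified, 14.6 applies it consistently with 14.4, it errs on the conservative side, and these endpoints do not decide the primary objectives. That stands: a reader might infer a multiplicity error, and the documents do not support one.

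The second reply is that a 10-point gain depends on an input that the plan contradicts. This also stands. One explanation would be that the Handling and Comfort means in Table 8 are transposed. The gaps would then be 67.9 − 61 = 6.9 and 65.4 − 58 = 7.4, with power of 95.9% and 97.8% at n = 135 and one-sided 2.5%. Those values lie either side of Table 9's 97%. At n = 165 Bonferroni would already give Handling 96.8%, and Holm at most 98.4%. The documents cannot confirm a transposition, so it is only an illustration of how small the gain could be.

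Third, 14.6 plans a mixed model with a baseline covariate, which may reduce the residual SD and shrink the gain. The documents give no adjusted SD, so 15 to 18 is an assumption.

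Fourth, Holm is not free. Two 97.5% intervals have joint coverage of at least 95%. Under Holm the second interval's level depends on the data and that simple reading is lost. Wanting matched simultaneous intervals is a legitimate reason to keep Bonferroni.

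None of this removes the basic point: Holm rejects whenever Bonferroni does, under any correlation, at the same family-wise error.

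**Conclusion.** This is an inexpensive efficiency improvement, not a defect in error control. Given the co-primary precondition and a one-sample t-test at 165 completers, the gain in Handling power is about 10 points (64% to 74%) on Table 8 as printed. It is about 3 to 7 points at an assumed SD of 15 to 18, and about 1 to 2 points if Table 9's 97% is right. Comfort power does not fall and no extra subjects are needed.

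Two stronger readings go too far. One is that the gain is 64% to 74% at no cost: that quotes only the Table 8 case and overlooks the loss of matched simultaneous intervals. The other is that Holm repairs the power for Handling: even 74% is far from the 97% or 99% stated in 14.2. The conflict between Tables 8 and 9 is a separate and larger matter, which the choice between Bonferroni and Holm does not settle.

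**What to change.** In 14.4, 14.6 and the stand-alone SAP, replace Bonferroni with Holm. Test the endpoint with the smaller p-value against its threshold using the 97.5% CI; if it passes, test the other using the 95% CI; if it does not, stop. Leave the co-primary precondition and the overall two-sided 5% unchanged.

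Make the change before database lock, which is when 14.1 requires the SAP to be final. Since 5.2 leaves sponsor personnel aware of lens identity, record that it was made before any Handling or Comfort results were summarised.

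The cost is a few sentences. The two decision intervals may carry different levels and lose their simple joint coverage, but 97.5% CIs for both endpoints can still be reported descriptively. In the same edit, align the one-sided 2.5% in 14.2 with the decision rule adopted. Separately, reconcile Table 8 with Table 9 and restate the Handling and Comfort power.

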14.5. Primary Analysis

Methodology regarding the plan for testing and/or handling statistical associations between co-primary safety and/or efficacy endpoints will be documented in the SAP.

Co-Primary Safety Analyses:

All primary safety analysis will be conducted on the safety population.

Grade 3 or Higher SLF

Grade 3 of Higher SLFs will be analyzed using a Bayesian beta-binomial model with correlated binary data.⁸

The Model:

Let \mathbb{Y}_1 and \mathbb{Y}_2 denote the binary outcomes of lens fit acceptance (Yes/No) in left and right eyes, respectively, across dispensing and follow-up visits when wearing the test lens. Considering the correlation, $\rho\rho$, between \mathbb{Y}_1 and \mathbb{Y}_2 , the distribution of the sum $YY = \mathbb{Y}_1 + \mathbb{Y}_2$ is obtained by the mixture of two variables. One of them follow a binomial distribution $BB\BBB(2, \rho\rho)$ with mixing probability $(1 - \rho\rho)$ and the other one follows a modified Bernoulli distribution, $MMBB\BBB(1 - \rho\rho)$, taking value 0 and 2 rather than conventional 0 and 1, with mixing probability $\rho\rho$:

$$PP(YY = yy | \rho\rho, \rho\rho) = (1 - \rho\rho)BB\BBB(2, \rho\rho)I_{AA1} + \rho\rho MMBB\BBB(1 - \rho\rho)I_{AA2},$$

where $I_{AA1} = \{0, 1, 2\}$, $I_{AA2} = \{0, 2\}$ and $\rho\rho$ is the probability of success (i.e., acceptable lens fitting).

To overcome the complexity of the mixture likelihood a latent variable ZZ_{ii} , $i = 1, 2$ is introduced in the model to indicate in which component of the model the observation yy_{ii} , $i=1, 2$, belongs to, that is,

$$ZZ = \begin{cases} 1, & \text{if the observation belong to the MBern}(p), \\ 0, & \text{if the observation belong to the Bin}(2, p) \end{cases}$$

The joint distribution of the augmented data (YY_{ii}, ZZ_{ii}) , $BB = 1, 2$, is given by

$$P(Y = y, Z = z | p, \rho) = \rho^{z_i} p^{y_i z_i / 2} (1 - p)^{(2 - y_i) z_i / 2} (1 - \rho)^{1 - z_i} \prod_{i=1}^2 p_{y_i}^{y_i(1 - z_i)} (1 - p)^{(2 - y_i)(1 - z_i)}$$

The probability p links to the regression variables through a logit transformation as follow:

$$\text{logit}(p) = \beta_0 + \beta_1 \text{lens}$$

It is assumed that β_0 , β_1 and $\rho\rho$ to be independent with a non-informative prior $N(0, 1000)$ for β_0 and β_1 , and beta(0.5, 0.5) for $\rho\rho$. The Metropolis sampler algorithm as implemented in the SAS/STAT MCMC Procedure⁷ will be used to estimate the posterior distributions of the parameters $(\beta_0, \beta_1, \rho\rho)$. Inferences will be made based on a posterior credible interval for the relevant parameters.

Bayesian Estimation and Statistical Evaluation of Hypothesis:

Superiority of the test lens relative to the pre-defined threshold with respect to grade 3 or higher will be evaluated using Bayesian statistics.

Primary Safety Hypothesis 1:

The null and alternative hypotheses for evaluating superiority of the test lens relative to 5% are as follows:

$$H_0: \rho\rho_T \geq 5\%$$

$$H_A: \rho\rho_T < 5\%,$$

Clinical Study Protocol
Johnson & Johnson Vision Care, Inc.

where p_{pT} is the probability of a grade 3 or higher SLF across all study visits for test lens. Based on Bayesian posterior probability distribution of the proportion pp_{TT} , superiority is interpreted as 95% probability of test being statistically lower than the threshold of 5% (i.e., $p_{pT} < 0.05$). If the upper bound of the 95% central posterior credible interval is below 0.05, it can be concluded that there is 95% probability that the test lens is superior to 5% (statistically less than) based on the observed sample.

In the case of zero clinically significant SLF, a Bayesian hierarchical model accounting for zero-event problem will be considered.⁸

Acceptable Lens Fitting

Lens fit acceptance will be analyzed using a Bayesian beta-binomial model with correlated binary data.⁸

Bayesian Estimation and Statistical Evaluation of Hypothesis:

Superiority of the test lens relative to the pre-defined threshold with respect to acceptable lens fitting will be evaluated using Bayesian statistics.

Primary Safety Hypothesis 2:

The null and alternative hypotheses for evaluating superiority of the test lens relative to 80% are as follows:

$$\begin{aligned} H_0: p_{pT} &\leq 80\% \\ H_{AA}: p_{pT} &> 80\%, \end{aligned}$$

where p_{pT} is the probability of event (i.e., probability of acceptable lens fitting while wearing the test lens). Based on Bayesian posterior probability distribution of the proportion pp_{TT} , superiority is interpreted as 95% probability of the test lens being statistically larger than the pre-defined threshold of 80% (i.e., $p_{pT} > 80$) with respect to acceptable lens fitting rate. If the lower bound of the 95% central posterior credible interval is above 80%, it can be concluded that there is 95% probability that the test lens is superior to the 80% threshold (statistically greater) based on the observed sample.

In the case of all eyes have an acceptable lens fit (i.e., zero unacceptable lens fits), a Bayesian hierarchical model accounting for zero-event problem will be considered.⁸ Details of this model will be provided in the stand-alone SAP.

Co-Primary Efficacy Analyses

Visual Acuity (VA)

Distance, monocular, high-luminance, high-contrast (HLHC), VA after 1 week of lens wear will be analyzed using a linear mixed model. Sequence of lens wear, lens type and period will be included in the model as fixed effects. Subject characteristics such as, gender, age and/or cylinder power may be included in the model if appropriate. Site ID and subject nested within site will be included in the model as random effects (G-side). The residual error between measurements within the same subject across study period will be modeled using an unstructured (UN) covariance structure. If the model fails to converge with a UN covariance, then a compound systemic (CS) covariance structure will be used. The Kenward and Roger Method will be used for the denominator degrees of freedom.¹¹ Visual Acuity scores will be estimated using 95% confidence intervals (CI) constructed for the least-square means (LSM).

Primary Efficacy Hypothesis 1:

The null and alternative hypothesis for distance monocular HLHC VA to test for superiority of test relative to the threshold 0.0 logMAR are as follows:

$$\begin{aligned} H_{00}: \mu_{TTTTTTTT} &\geq 0 \text{ logMAR} \\ H_{AA}: \mu_{TTTTTTTT} &< 0 \text{ logMAR} \end{aligned}$$

Clinical Study Protocol
Johnson & Johnson Vision Care, Inc.

Where $\mu_{TTTTTTTT}$, represents the population mean for test lens after 1-week of lens wear with respect to distance monocular HLHC VA. Superiority will be declared if the upper limit of the 95% CI is below 0.0.

Toric Lens Orientation and Rotational Stability at Least 15- Minutes Following Lens Settling

Absolute toric lens orientation (degrees) will be dichotomized as $Y=1$ if the absolute lens orientation (degrees) $\leq 10^\circ$ and $Y=0$, otherwise. Rotational stability will be quantified by lens stability with blinks (degrees). Lens stability will be dichotomized as $Z=1$ if the lens stability with blinks (degrees) $\leq 5^\circ$ and $Z=0$, otherwise.

Y and Z will be analyzed separately using a generalized linear mixed model with a binary distribution and the logit as the link function. Sequence of lens wear, lens type and period will be included in the model as fixed effects. Subject characteristics such as, gender, age and/or cylinder power may be included in the model if appropriate. Site ID and subject nested within site will be included in the model as random effects (G-side). The residual error between measurements within the same subject across study period will be modeled using an unstructured (UN) covariance structure. If the model fails to converge with a UN covariance, then a compound systemic (CS) covariance structure will be used. The Kenward and Roger Method will be used for the denominator degrees of freedom.¹¹

Primary Efficacy Hypothesis 2:

The null and alternative hypothesis to test for superiority of absolute lens orientation $\leq 10^\circ$ for the test lens relative to the threshold 80% are as follows:

$$\begin{aligned} H_{H_0}: pp_{TTTTTTTT} &\leq 80\% \\ H_{H_A}: pp_{TTTTTTTT} &> 80\% \end{aligned}$$

Where $pp_{TTTTTTTT}$, represents the population percentage for the percentage of eyes wearing the test lens with absolute lens orientation $\leq 10^\circ$. Superiority will be declared if the lower limit of the 95% CI is above 80.

Depending on the observed response rates for the percentage of subjects' eyes with absolute lens orientation $\leq 10^\circ$ and the percentage of subjects' eyes with lens stability with blinks $\leq 5^\circ$, a Bayesian hierarchical model accounting for zero event problem may be considered (i.e., 0% of eyes with toric rotation $>10^\circ$ [or lens stability $>5^\circ$]) . Details of this model will be provided in the stand-alone SAP.

Primary Efficacy Hypothesis 3:

The null and alternative hypothesis to test for superiority of lens stability with blinks $\leq 5^\circ$ for the test lens relative to the threshold 80% are as follows:

$$\begin{aligned} H_{H_0}: pp_{TTTTTTTT} &\leq 80\% \\ H_{H_A}: pp_{TTTTTTTT} &> 80\% \end{aligned}$$

Where $pp_{TTTTTTTT}$, represents the population percentage for the percentage of eyes wearing the test lens with lens stability with blinks $\leq 5^\circ$. Superiority will be declared if the lower limit of the 95% CI is above 80.

CLUE Vision Scores

CLUE vision scores after 1 week of lens wear will be analyzed using a linear mixed model adjusting for baseline scores as a covariate. Sequence of lens wear, lens type and period will be included in the model as fixed effects. Subject characteristics such as, gender, age and/or cylinder power may be included in the model if appropriate. Site ID will be included in the model as a random effect (G-side). The residual error between measurements within the same subject will be modeled using an unstructured (UN) covariance structure. If the model fails to converge with a UN covariance, then a compound systemic (CS) covariance structure will be used. The Kenward and Roger Method will be used for the denominator degrees of freedom.¹¹ CLUE Vision Scores estimates for each study lens will be estimated using 95% confidence intervals (CI) constructed for the least-square means (LSM).

Clinical Study Protocol
Johnson & Johnson Vision Care, Inc.

Primary Efficacy Hypothesis 4:

The null and alternative hypothesis to test for superiority of CLUE vision score for the test lens relative to the threshold 62 are as follows:

$$\begin{aligned} H_0: \mu_{TTTTTTTT} &\leq 62 \\ H_A: \mu_{TTTTTTTT} &> 62 \end{aligned}$$

Where $\mu_{TTTTTTTT}$, represents the population mean for test lens after 1 week of lens wear with respect to CLUE vision scores. Superiority will be declared if the lower limit of the 95% CI is above 62.

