2.2. Endpoints

Primary Safety Endpoints:

Slit Lamp Findings (SLF)

SLFs (Grade 3 or higher) related to study lens wear will be assessed for each eye at all study visits (scheduled and unscheduled). SLFs will be evaluated and graded using the FDA Grading scale from 0 to 4, where Grade 0 represents the absence of findings and 1 to 4 representing successively worse findings. The percentage of eyes with Grade 3 or higher SLF will be analyzed and will include corneal infiltrates. See [REDACTED] in Appendix D for more details on the collection of SLFs.

Acceptable Lens Fit

Acceptable lens fit will be assessed at all study visits (scheduled and unscheduled) for each subject eye. Acceptable fit is a binary response where Y=1 if lens fit is acceptable and Y=0 otherwise. Lens fit will be deemed unacceptable if any one of the following criteria are met:

- limbal exposure at primary gaze or with extreme eye movement;
- edge lift;
- excessive movement in primary up gaze;
- insufficient movement in all three of the following conditions: primary gaze, up gaze, and push up test.

Eyes with multiple unacceptable fitting events will be counted only once. See [REDACTED] in Appendix H for additional details regarding lens fit assessments.

Primary Efficacy Endpoints:

Visual Acuity (logMAR)

Visual acuity (VA) will be assessed monocularly at the 1-week follow-up evaluation under high-luminance high-contrast (HLHC) conditions at a test distance of 4 meters using ETDRS Charts. See [REDACTED] in Appendix D for details regarding the collection of visual acuity.

Toric Lens Orientation

Toric lens orientation (scribe mark position relative to 6 o'clock) will be assessed for each eye at 1, 3 and at least 15 minutes after lens insertion at the fitting visit, and at the 1-week follow-up visit. However, lens orientation at least 15 minutes after lens insertion at the fitting visit is the primary endpoint. Lens orientation is a binary response where Y=1 if the absolute lens orientation is $\leq 10^\circ$ and Y=0 otherwise. See [REDACTED] in Appendix D for details regarding the collection of absolute toric lens orientation.

Rotational Stability

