14. STATISTICAL METHODS

14.1. General Considerations

Statistical Analysis will be undertaken by the sponsor or under the authority of the sponsor. A general description of the statistical methods to be implemented in this clinical trial is outlined below. More details will be included in the stand-alone Statistical Analysis Plan (SAP). The SAP will be developed and finalized prior to database lock.

All data summaries and statistical analyses will be performed using the SAS software Version 9.4 SAS Institute, Cary, NC⁷. Throughout the analysis of data, the results for each subject/eye will be used when available for summarization and statistical analysis. For the analysis of co-primary safety endpoints, unscheduled visits will be summarized separately and will not be excluded from the statistical analysis. However, for the analysis of co-primary efficacy endpoints and secondary endpoints, unscheduled visits will be summarized separately and excluded from the statistical analysis.

Summary tables (descriptive statistics and/or frequency tables) will be provided for all baseline variables, efficacy variables and safety variables as appropriate. Continuous variables will be summarized with descriptive statistics

Clinical Study Protocol
Johnson & Johnson Vision Care, Inc.

(n, mean, standard deviation(SD), median, minimum and maximum). Frequency count and percentage of subject.s or eyes within each catego1y will be provided for categorical data.

Summaries will be presented by separately for each time point (baseline, fitting and 1-week follow-up) and will be perfo1med separately by completion status (Safety Population, Per-Protocol Population or Intent-to-treat, when appropriate).

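### The model paragraph for Grade 3 or higher slit-lamp findings in 14.5 defines lens-fit acceptance over a narrower visit window, contradicting Hypothesis 1 and the endpoint

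*Combined protocol and SAP*

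**What the plan says.** Section 14.5 opens the SLF analysis correctly: "SLFs will be analyzed using a Bayesian beta-binomial model with correlated binary data". The model paragraph that follows then describes a different endpoint. Y1 and Y2 "denote the binary outcomes of lens fit acceptance (Yes/No) in left and right eyes", the visits are "across dispensing and follow-up visits when wearing the test lens", and the modelled parameter "is the probability of success (i.e., acceptable lens fitting").

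Primary Safety Hypothesis 1, in the same subsection, sets the null at 5% or more and the alternative at below 5% for a parameter that "is the probability of a grade 3 or higher SLF across all study visits for test lens". The decision rule begins "If the upper bound of the 95% central posterior credible interval is below 0.05".

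The rest of the plan agrees with the hypothesis. Section 2.2 states: "SLFs (Grade 3 or higher) related to study lens wear will be assessed for each eye at all study visits (scheduled and unscheduled"). Section 14.1 says of the co-primary safety endpoints that "unscheduled visits will be summarized separately and will not be excluded from the statistical analysis". Section 14.2 codes an eye as 1 when it has a clinically significant SLF. Section 7.3 collects slit-lamp findings at unscheduled visits. The lens-fit subsection of 14.5 names the same type of model but gives no definition of Y1, Y2 or p for fit beyond the one in its hypothesis.

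**The concern.** The symbol p has two meanings within one analysis. In the model it is an event hoped to be nearly universal (an acceptable fit); in the hypothesis it is an event hoped to be rare (a Grade 3 or higher finding). The lens-fit sentence appears to have been carried into the SLF subsection, which leaves SLF with the wrong definition and lens fit with none.

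Under 14.4, both safety hypotheses must be met before any efficacy hypothesis is tested, and this paragraph is the only full model statement for either. It should therefore be programmable as printed. There is also a second step to the repair. Someone who replaces only the outcome name would keep a visit window that does not match the SLF endpoint.

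**Working it through.** The defect is textual, so the main check sets the passages side by side.

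| Element | Model paragraph, 14.5 | Elsewhere in the plan |
|---|---|---|
| Eye-level outcome | Lens fit acceptable, yes or no | Grade 3 or higher SLF (2.2, 2.3, 14.2, Hypothesis 1) |
| Meaning of p | Probability of acceptable fit | Probability of Grade 3 or higher SLF (Hypothesis 1) |
| Favourable direction | High (fit is tested against 80%) | Low (SLF is tested against 5%) |
| Visits | Dispensing and follow-up | All study visits (Hypothesis 1), scheduled and unscheduled (2.2), unscheduled kept in (14.1) |

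**What the literal reading does.** Inputs: acceptable-fit rate 99% and between-eye correlation 0.70 (14.2), n = 100 subjects (Table 9), Beta(0.5, 0.5) prior on the correlation (14.5). For the number of eyes Y = Y1 + Y2, the mixture in 14.5 gives:

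- P(Y = 0) = (1 − ρ)(1 − p)² + ρ(1 − p) = 0.3 × 0.0001 + 0.7 × 0.01 = 0.00703
- P(Y = 1) = (1 − ρ) × 2p(1 − p) = 0.3 × 0.0198 = 0.00594
- P(Y = 2) = (1 − ρ)p² + ρp = 0.3 × 0.9801 + 0.7 × 0.99 = 0.98703

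The expected count is 200 × 0.99 = 198 acceptable eyes out of 200, against a rule that needs the upper credible bound for p below 0.05. In 200 simulated trials, with the posterior computed on a grid for the test lens alone and a Jeffreys prior on p, the rule was met 0 times. The plan's own prior is normal on the logit scale, but with data this far from 5% the choice is immaterial. Reading the parameter as 1 − p does not rescue the text: that is the probability of an unacceptable fit, which is still not an SLF.

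**The window, if only the outcome name is replaced.** Scheduled biomicroscopy at the dispensing visits comes before the study lens goes in: step 1.12 precedes insertion at step 1.16, and step 3.5 precedes Lens Fitting #2. A scheduled slit-lamp grade at a dispensing visit therefore cannot reflect the lens about to be fitted. For subjects who wear the test lens first, the Visit 3 examination follows test wear and washout but belongs to the visit that dispenses the control. Section 14.5 gives no rule for attributing a finding there. Unscheduled visits are not named in the sentence at all.

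**The displaced lens-fit definition.** Its visit scope differs in three places: all scheduled and unscheduled visits (2.2), the dispensing visit (2.3), and dispensing plus follow-up (the 14.5 model sentence). Table 3 and the steps in 7.2 schedule the general fit assessment only at Visits 1 and 3.

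**The case against.** The strongest reply is that no one could be misled. The subsection heading, lead sentence, hypotheses, 5% threshold, zero-event clause and 14.2 coding all name SLF, and the literal reading defeats itself so completely that an analyst would notice at once. The visit window is part of the same misplaced sentence, so it is one slip rather than two. Section 14.1 also defers detail to a stand-alone SAP, which is not part of the text available here and may already state the outcome correctly.

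Much of this stands. The intended endpoint is not in doubt, and the defect is best described as an internal contradiction rather than a decision to analyse the wrong outcome. It does not remove the need for correction: the paragraph is the only place in 14.5 that defines Y1, Y2 and p, and lens fit has no outcome definition of its own to compare it with.

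Two stronger readings are tempting and are not supported. A reader might infer that the plan leaves out unscheduled visits. It does not: 2.2 includes them, 14.1 keeps them in the safety analysis, 7.3 collects the data, and Hypothesis 1 covers all study visits.

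A reader might also infer that one missed case would reverse the safety conclusion. With 165 subjects and the logit prior (1000 read as a variance), three bilaterally affected subjects give an upper bound of about 4.1% and four give about 5.0%. But 165 is the completer target, while the analysis uses the safety population. Four bilateral cases pass at 172 subjects (about 4.8%) and at 180 (about 4.6%), and nine unilateral cases still pass at 165. The historical rate in Table 8 is 0%. The reversal also requires dropping a case contrary to 14.1. It does not measure this defect.

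**Conclusion.** The point holds as an internal contradiction. The SLF model paragraph in 14.5 is wrong in its outcome and in the meaning of p, and its visit window is narrower than the endpoint, the general analysis rule and the hypothesis. Literal application could not meet the 5% rule (0 of 200 simulated trials, assuming 99% acceptable fit, correlation 0.70 and n = 100). That shows the text cannot be followed as printed; it is not an estimate of bias in the trial's result. No effect on the SLF rate or on the chance of passing is claimed, since the rest of the plan names the right endpoint and visits. The correction is worth making because this is the first step of the testing sequence and its only printed model.

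**What to change.** In 14.5 and the stand-alone SAP:

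1. Replace the definition under the SLF heading: Y1 and Y2 equal 1 if that eye has any study-lens-related Grade 3 or higher SLF at any scheduled or unscheduled visit attributable to test-lens wear, after test-lens insertion, and 0 otherwise; p is the probability of such a finding.
2. State how a finding first seen at the Visit 3 examination is attributed when the test lens was worn first.
3. Move the fit-acceptance definition of Y1, Y2 and p to the lens-fit subsection, and reconcile its visits across 2.2, 2.3 and 14.5, checking that fit is actually recorded at each visit named.

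The cost is about one paragraph. It needs no new data for SLF and no change to the sample size, threshold or decision rule. Section 14.1 has the SAP finalised before database lock, so the change can be made before then.
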